Research Proposal

LU 206338

Evaluation of Gadoterate in Patients with Renal Dysfunction

Version 5 dated 1Nov2018

Principal Investigator: [name]

Sub-investigator: [name]

Sponsor: Guerbet Pharmaceuticals

IND Number: 126009

Background and Significance

Magnetic Resonance Imaging (MRI) has become an indispensable tool in disease diagnosis and patient management. Imaging with MRI yields the highest quality tissue characterization in most regions of the body, and does so without the potential harmful effects of ionizing radiation. A discussion of MRI technology is beyond the scope of this proposal, but, briefly, MRI utilizes both fixed and dynamic magnetic fields to excite the body's water molecules and extract images of the local tissue environment. Gadolinium (Gd) is a naturally-occurring element which is paramagnetic – meaning it can change the local magnetic field. Therefore, tissue infused with a chemical agent containing Gadolinium will appear more prominent on an MR image. Gadolinium-based intravenous contrast agents (GBCA) are therefore widely used for enhancement of anatomic structures during magnetic resonance imaging (MRI) examinations. These agents allow more detailed and complete characterization of anatomy and disease processes. For example, the degree of viability within a treated tumor can be evaluated based upon residual Gadolinium enhancement within the lesion, or a fluid collection can be characterized as infected if it has enhancement around its periphery. However, GBCAs have been implicated in varying degrees of nephrotoxicity and, very seldomly, in a skin and organ fibrotic disorder called Nephrogenic Systemic Fibrosis (NSF) [1-7]. This condition is theorized to result from toxicity related to free Gadolinium (free Gd is toxic) that has become dissociated from its bound state in the larger contrast molecule. Decreased renal function theoretically results in longer circulation of the GBCA and thus a greater likelihood of Gd dissociating and accumulating in tissues. The American College of Radiology therefore advises caution when using Gadolinium in patients with estimated glomerular filtration rates (GFR – a standard calculation of kidney function that estimates how much flow is filtrated through the kidney, based upon serum creatinine concentration, age, weight, and race) less than 60 ml/min and advises no routine use in GFR < 30 ml/min [7].

Gadoterate (DotaremTM) is a particular Gadolinium agent that has been widely used in Europe for over 24 years and has recently become commercially available in the U.S. Its chemical formulation confers significantly greater stability to the bound state of Gadolinium, compared with other GBCAs (Figure 1) [8-10]. Furthermore, experience based upon widespread clinical use in Europe, as well as data yielded by several smaller studies, strongly indicate that Gadoterate is safe in patients with GFR < 60 and even in patients with GFR < 30 [11-15]. Of note, there have been no cases of NSF in over 43 million administrations in Europe [14], and a German post-marketing analysis of more than 84,000 patients demonstrated no adverse renal events (general adverse events were < 0.3%) despite over 750 patients defined as having a risk factor of chronic renal disease [12]. And, a study of over 500 dialysis patients revealed no cases of NSF after 6 months [15]. It is also important to highlight that even in populations with reduced GFR and end stage renal disease (ESRD) who received serial high-doses of significantly less-stable Gadolinium contrast agents, only a 3-4% rate of NSF has been reported [7,16]. The risk of using a more stable GBCA within strict dosing guidelines is much less. (More generally, there have been an estimated 200 million Gadolinium administrations, with fewer than 1000 cases of NSF). While the risk

of contrast administration can never be entirely ignored, it is important to be cognizant of these conclusions when considering the suboptimal clinical care often afforded patients who do not receive Gadolinium contrast exams. For example, definitive diagnosis of hepatocellular carcinoma in a patient with cirrhosis, or of renal cell carcinoma in a patient with uncharacterized renal lesions, is all but limited to contrast-enhanced imaging, and manifests in dramatically disparate therapy compared with less definitive diagnosis (therapy initiation vs. serial follow-up imaging or invasive biopsy). Therefore, the benefits of having a GBCA on formulary, with which Gadolinium-enhanced MRI exams could be performed on any patient, regardless of GFR, would be significant to patient-care. The potential scale is significant due to the number of patients that fall into this category in our institution's catchment population as well as across the U.S. [17]. However, widespread misunderstanding of the chemical and clinical data has instilled fear of both medical and legal complications and has precluded current radiology practices from using GBCAs in patients with GFR<30. Currently, we estimate in excess of 800 exams that are annually performed at our institution without Gadolinium enhancement – and thus suboptimally - due to GFR restrictions. Our goal is to therefore gather robust single-site pilot data at Loyola University Medical Center and then proceed to a larger multi-site trial demonstrating the safety and utility of Gadoterate in this particular patient population.

Hypothesis and Study Aims

Hypothesis 1: Use of Gadoterate in a population of patients with GFR<30 will not result in statistically-significant numbers of adverse renal events, defined by decreased GFR and/or NSF.

Hypothesis 2: Use of Gadoterate in a population of patients with GFR<30 will result in more definitive radiologic interpretations and improved clinical care compared with those associated with non-contrast images only. Metrics of evaluation include improved timeliness and quality of disease treatment, as well as fewer follow-up imaging studies with greater specificity (see below).

Specific Aim 1: Establish Gadoterate-based MRI protocols for GFR<30 patients, and establish database (and analytic models) of pre and post-exam laboratory data as well as relevant demographic data.

Specific Aim 2: Establish database of comparative radiologic findings, clinical care decisions, therapy outcomes, and downstream imaging costs, for radiology interpretations based upon unenhanced vs. Gadoterate-enhanced MRI images.

Study Design

The study design is straightforward, and will consist of 2 equal-sized cohorts of patients, all of whom have GFR of < 30 ml/min, but are not on dialysis, and all of whom are being sent for an MRI examination in the course of routine clinical evaluation of one of the following indications: suspected or known head/neck/brain mass, hepatic mass, renal mass, pancreatic mass, or prostate mass, as well as evaluation of carotid or abdominopelvic vasculature. These relatively few indications constitute the vast majority of indications for contrast MRI in our health system, similar to most institutions. As such, there will be significant statistical representation of these indications in each cohort. At the same time, limiting the study to these indications will allow greater organizational structure, with more focused points of enrollment. Note that each of the corresponding clinical departments has expressed significant interest in participation; patients will be enrolled over a two year period from the hepatology, surgery, urology, neurology, and neurosurgical services at Loyola. Following IRB approval and informed consent, patients in the first group will receive MRI exams with no Gadolinium contrast, while the other group will receive standard pre-contrast *and* Gadoterate-enhanced acquisitions (0.2 mL/kg). MRI protocols utilized in the study will be comprised of the standard Body protocols (routine abdomen, liver-pancreas, renal, prostate,

angiography) as well as the standard Neurologic exam protocols (routine brain, orbital, brainstem, neck, angiography).

Ineligibility criteria will include pregnancy, lactation, planned initiation of chemotherapy or surgery within 72 hours of the MRI exam, hemodynamic instability or acute coronary syndrome, history of nephrotoxic medication within 2 weeks of the exam (Amphotericin B, Lithium, Pentamidine, Aminoglycosides, Acyclovir, Gancyclovir, or Foscavir), and age less than 18 years.

Aim 1:

Each patient's GFR will be recorded prior to the exams and 48-72 hours after scanning. In addition, each patient will be contacted at baseline as well as 6 weeks, 3 months, and 6 months post-scan to comprehensively evaluate for any symptoms or signs of NSF (see attached sheet) [19]. If at any point a patient's follow-up interviews indicate they might be experiencing symptoms of NSF, or if their post-MRI research blood draw indicates deteriorating renal function, the study PI will be notified and the patient will be referred for further medical evaluation, if necessary. All relevant demographics, such as hypertension, diabetes, coronary artery disease, and liver disease, will be recorded. The data will be analyzed, using standard statistical methods, for any significant and disparate variations in renal function.

Aim 2:

Each MRI exam will be independently interpreted by 2 participating sub-specialty-trained (either neuro or body) radiologists. To limit bias, the readers will initially be blinded to history and prior exams and their respective interpretations recorded in the research database (history and prior exams will subsequently be provided, as usual, for the final interpretations used in clinical care). The interpretations and inter-reader correlation will be recorded for each exam. Via Loyola electronic medical record (EMR) we will record the chronology of all subsequent related diagnoses, imaging studies, pathology results, therapies, and related costs (defined as gross hospital charge), within the study period (1-2 years) and for one year afterward. These data will be analyzed to compare differential outcomes between the non-contrast and contrast cohorts.

To further explore the concept of Gadoterate-based differential outcomes, two separate interpretations for each Gadoterate-enhanced MRI will be recorded in the research database: an interpretation based upon only the non-contrast images and the full interpretation of the whole exam (non-contrast + contrast images). We will subsequently record the *predicted* outcome data, as described above (diagnoses, subsequent imaging studies, pathology results, therapies, and projected related costs), that would be associated with the more limited interpretation of the non-contrast images. Comparison to the actual outcomes of that patient will subsequently be analyzed. This is both feasible and straightforward since the vast majority of the clinical MRI indications in this study have a well-defined diagnostic/therapeutic pathway – i.e. a solitary liver lesion demonstrated to be malignant by contrast MRI would result in chemo-embolization, whereas an indeterminate result based on non-contrast would lead to a liver biopsy [18]. Another example: Cystic renal lesions which cannot be completely characterized without contrast are typically followed with serial imaging exams to check for growth, whereas demonstration of a simple cyst by contrast-enhanced exam will typically result in no further imaging.

Statistics:

Previously-tested GBCAs in chronic kidney failure patients have resulted in 10-25% rates of decreased GFR, depending upon the study, with most investigations recording rates in the range of ~15% [5]. Based upon various data thus far (noted above), the rate is expected to be no more than 5% using Gadoterate;

therefore if we wish to detect a significantly lower rate of renal complications with a power of 90% and a 5% significance, then a sample size of approximately 136 patients receiving Gadoterate is properly powered to address Aim 1. The non-Gadoterate control arm does not need to be as large for analysis of Aim 1, however, it will consist of 136 patients as well, to properly power analysis of Aim 2. This number is expected to be more than sufficient considering that significant interpretive and outcome differentials are anticipated at a far greater rate than 5%, between the non-contrast image and contrast image evaluations.

Study Procedures

Subject selection

Inclusion Criteria: GFR less than 30 ml/min, but not on dialysis, with indications for MRI as described above. GFR will be calculated in the same fashion as in current use in our department:

$$\text{eGFR} = \frac{(140 - \text{Age}) \times \text{Mass (kg)} \times (0.89 \text{ if female})}{72 \times \text{serum creatinine (mg/dL)}}$$

Exclusion Criteria: Pregnant and lactating females; planned initiation of chemotherapy or surgery within 72 hours of the MRI exam; hemodynamic instability or acute coronary syndrome; history of the following nephrotoxic medications within 2 weeks of the exam: Amphotericin B, Lithium, Pentamidine, Aminoglycosides, Acyclovir, Gancyclovir, or Foscavir; age less than 18 years.

Note that many patients within the inclusion criteria may have pre-existing conditions which could, theoretically, cause a GFR decrease unrelated to the Gadoterate in the 48-72 hour post-injection window; however, such cases will be statistically represented in both cohorts and, as such, are not expected to affect the comparisons between the two populations due to the sufficient statistical power of the study.

Recruitment

Patient recruitment will occur via two complementary mechanisms: In the clinician office when the study is ordered and via the research nurse and/or study coordinator. It is expected that a significant component of patients will be recruited into the study by the clinicians in the participating departments. Education of clinicians in these departments is ongoing at this time and all have been enthusiastic about participating. In addition, the nurse coordinator will review the radiology informatics system, on a daily basis, to identify all eligible patients for whom non-contrast MRIs have been ordered due to GFR concerns. In such cases the nurse coordinator will contact the study PI to determine eligibility. If the patient meets eligibility criteria, the study PI will confirm with the patient's ordering physician. The patient will be contacted and the study PI, sub-investigator, or other appropriate study staff will explain the study, with its risks and benefits, to the patient at least 8 hours prior to the MRI exam. The study PI or sub-investigator will contact the ordering physician prior to the date of the exam to obtain an updated order allowing for contrast MRI. Signature of the consent form itself will then be available for the patient at the time of the exam. In either of these scenarios a patient who does not want Gadoterate contrast will receive the usual non-contrast MRI.

In reviewing the radiology informatics system, the coordinator may identify a patient who meets eligibility criteria and whose GFR has already been obtained through standard care, but who already had a standard MRI completed without contrast within the past 24 hours. If this occurs, the PI will be notified to determine if it is appropriate to contact the patient and obtain consent post-MRI. If the patient consents

to the study, they would be placed into the control (non-contrast) group and undergo the remaining study activities of post-MRI blood draw and questionnaires at baseline, 6 weeks, 3 months and 6 months.

Consent

A discussion of the study, including discussion of risks and benefits, will be conducted by the study staff (PI, sub-investigator, research nurse, or study coordinator) with the patient at least 8 hours prior to the exam (except, as noted above, in the event a patient is identified post-exam). The consent form can then be signed at the time of the exam. Consent will be obtained following our institution's policies and procedures. Patient eligibility will be confirmed prior to study enrollment.

If a patient is unable to give informed consent due to cognitive dysfunction (for example, stroke, trauma, or encephalopathy from liver failure), their guardian, spouse, parent, or the individual holding power of attorney for their healthcare will be approached to consent for the patient. If the patient regains his or her ability to make decisions, he or she will be informed about the study and asked for a decision about continued participation. In the event the patient does not regain his or her ability to make decisions at the time the questionnaires are administered, the individual who consented on behalf of the patient will be asked to answer the symptom questionnaires on the patient's behalf.

Recruitment materials

No advertising will be provided. Written material will consist of the ICD. \$25 will be provided to patients as compensation for their 2-3 day return visit (blood-draw) and \$5 for parking.

Selection

It is expected that a significant percentage of patients fulfilling the eligibility criteria will nevertheless choose to decline receiving Gadoterate and receive the default non-contrast exam. These patients will be asked to take part as the non-contrast arm of the study.

Gadoterate

Gadoterate will be the only contrast agent used. There is no placebo and no blinding is needed. Gadoterate will be provided by Guerbet pharmaceuticals and will be stored in the identical fashion that all Gadolinium agents are stored in the department (see attached package insert). Gadoterate will be administered according to its standard weight-based protocol, 0.2 mL/kg [8].

Administrative Organization

This will be a single site study conducted at Loyola University Medical Center. Patient recruitment and participation from the referring clinicians in the hepatology, neurosurgery, neurology, neurosurgery, and urology divisions will be coordinated by an MRI nurse coordinator, who will devote 10% time to this project. In addition, all blood draws and patient follow up will be coordinated by the nurse coordinator. All imaging will be conducted on-site. The standard LUMC laboratory locations and procedures will be used to calculate GFR from the patients' serum.

The clinical research office (CRO) will assist with statistical data analysis.

Safety and Monitoring

As with any intravenous contrast agent, numerous nonspecific adverse (mostly allergic-type) reactions are possible, though rare (see attached package insert), for Gadoterate, and no more common than in any other agent in clinical use. The most serious adverse event is difficulty breathing. Patient safety related to

such events will be monitored by direct technician and nurse supervision at the time of the exam and in the immediate period following – this is standard department protocol for all contrast MRI exams.

The main additional serious adverse reaction is the one being specifically monitored in this study - renal toxicity. Monitoring of this will be done by 48-72 hour post-exam serum creatinine evaluation, as described above. In addition, long-term toxicity in the form of NSF will be evaluated by detailed phone follow-up, designed to identify any potential signs of NSF (see Figure 2). In the event of a positive response to 3 or more of the questions in the questionnaire, the patient will be assisted in scheduling a Dermatology appointment at LUMC.

The PI ([name]) and the nurse coordinator will be responsible for tracking and assessing any adverse events.

Reporting of Adverse Events or Unanticipated Problems involving Risk to Participants or Others:

Any adverse events, as described above or unanticipated, involving risk to participants, will be promptly submitted to the IRB in accordance with established guidelines.

In addition, all data related to renal function and NSF will be routinely reviewed by the PI every 3 months.

Analysis

Image analysis: As described above, each MRI exam will be independently interpreted by 2 participating sub-specialty-trained (either neuro or body) radiologists, with the readers blinded to history and prior exams. For both contrast and non-contrast exams, the images will be viewed in the standard clinical fashion (Intellispace PACS system). For the contrast exams, the interpreting radiologists will first render an evaluation based upon *only* the non-contrast images - these interpretations will be recorded only within the research database. As described earlier, this will enable evaluation of the added advantages of the contrast agent. The overall contrast-exam interpretations, as well as the interpretations of the non-contrast exams, will be recorded in both the research database as well as dictated into the EMR, since these studies will be ordered as part of clinical care. The CRO will assist in analyzing trends of inter-reader correlation and variability.

Outcomes analysis: We will analyze the differential outcomes, between the two cohorts, as well as between the projected and actual outcomes within the contrast cohort, in these specific categories: diagnoses, number and types of subsequent imaging studies, pathology results, therapies, and related costs (defined as gross hospital charge), within the study period and extending 1 year afterward. The CRO will assist in analyzing variation within these metrics between the non-contrast vs. contrast cohorts. The CRO will also assist in analysis of variation between the projected outcomes and actual outcomes within the contrast cohort.

Risks vs Benefits

The risks particular to involving this patient population (GFR < 30 ml/min) in this trial are decreased renal function, including the possibility of the need for permanent dialysis, and NSF. However, extensive clinical experience and literature clearly support the fact that the chance of significant renal dysfunction is small and the chance of NSF is quite remote. On the other hand, the addition of Gadolinium contrast to an MRI exam is often of critical importance for determining accurate anatomic relationships, differentiating benign from malignant lesions or infected tissue from normal tissue, and determining resolving vs.

worsening disease. Patients who are ill and who therefore often need these important determinations from their MRI studies are often the ones unable to have Gadolinium contrast due to GFR concerns. Thus, while the risk is real, the benefits are clear and of immediate impact in numerous clinical situations. It is anticipated that patients involved in this study will be the recipients of such benefits. More generally, establishment of safe contrast-MRI protocols in this general population will contribute to advancement in the standard of care by which MRI is utilized for them, with these benefits potentially realized on a much more significant scale.

References

- [1] Thomsen HS: Nephrogenic systemic fibrosis: A serious late adverse reaction to gadodiamide. *Eur Radiol* 16: 2619–2621, 2006
- [4] Update on Magnetic Resonance Imaging (MRI) Contrast Agents Containing Gadolinium and Nephrogenic Fibrosing Dermopathy, 2006. Available at: http://www.fda.gov/cder/drug/advisory/gadolinium_agents_20061222.htm. Accessed November 1, 2008
- [5] Parazella M, Current Status of Gadolinium Toxicity in Patients with Kidney Disease; *Clin J Am Soc Nephrol* 4: 461–469, 2009.
- [6] Janus et al. Prevalence of nephrogenic systemic fibrosis in renal insufficiency patients: Results of the FINEST study, *Eur Journal Radiol*. 2010; 73:357-359.
- [7] ACR committee on Drugs and Contrast Media, ACR Manual on Contrast Media, Version 9, 2013

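### Hypothesis 1 words renal safety as an absence of significance, and the power claimed for the cohort comparison was never calculated; report the difference with its 95% interval

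*Combined protocol and SAP*

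**What the plan says.** - **Hypothesis and Study Aims, Hypothesis 1:** in patients with GFR below 30, Gadoterate "will not result in statistically-significant numbers of adverse renal events". No comparator, estimate or acceptable excess is named.
- **Study Design, Aim 1:** the data will be analysed "using standard statistical methods, for any significant and disparate variations in renal function". No test, effect measure or interval is given.
- **Statistics:** the sample size applies "if we wish to detect a significantly lower rate of renal complications" than that of other agents, with "most investigations recording rates in the range of ~15" per cent against at most 5% expected for Gadoterate, at 90% power and 5% significance. This gives about 136 Gadoterate patients. "The non-Gadoterate control arm does not need to be as large for analysis of Aim 1"; it is set at 136 for Aim 2.
- **Subject selection, note after the exclusion criteria:** GFR falls caused by pre-existing conditions "are not expected to affect the comparisons between the two populations due to the sufficient statistical power of the study".
- **Selection:** of patients who decline Gadoterate, "These patients will be asked to take part as the non-contrast arm of the study".
- **Analysis, Outcomes analysis:** the cohorts are compared "in these specific categories: diagnoses, number and types of subsequent imaging studies, pathology results, therapies, and related costs". Renal function is not listed. It appears later only as an item for monitoring, including the investigator's three-monthly review.

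**The concern.** Failing to find a significant difference is not evidence that there is none, least of all with few events. Two questions are run together here. One is whether Gadoterate does better than the rate reported for other agents; the plan sizes and tests that. The other is whether Gadoterate adds renal events over an unenhanced scan. The note on pre-existing conditions depends on the second question, but the plan neither sizes it nor says how it will be analysed.

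The same note also gives power a job it cannot do. More patients reduce random error. They do not remove systematic differences between patients who accept contrast and patients who decline it.

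The pilot could therefore report a rate below 15% and a non-significant cohort difference as renal safety, while its own data remain compatible with a clear excess. Background and Significance leaves the demonstration of safety to a later multi-site trial. What is at stake is what the pilot may claim and the estimate carried into that trial.

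**Working it through.** **Inputs.** From Statistics: 136 per cohort, reference rate 15%, expected Gadoterate rate 5%, 5% significance, 90% power. Sidedness is not stated. The documents give no event rate for unenhanced patients, so every control rate below is an assumption. A renal event is treated as yes/no, as in Hypothesis 1 and Statistics, and comparisons are unadjusted.

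**1. What the 136 is for.** A one-sample comparison with 15%, using the null variance and a two-sided 5% level, gives

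n = (1.960 + 1.282)² × 0.15 × 0.85 / 0.10² = 134,

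close to 136. The usual one-sample score formula gives 96. Comparing two cohorts at 15% v 5% with 90% power needs 188 per cohort two-sided or 153 one-sided. Two-sample formulas come near 136 (138 unpooled, 133 arcsine) only at 80% power, which is not the stated power.

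As a historical test, 136 is ample. At an exact lower tail of 2.5%, the 15% rate is rejected with 12 or fewer events (probability 0.0233 at 15%), and power at a true 5% is 98.1%.

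**2. Power of the cohort comparison.** Sum the product of two binomial probabilities (n = 136 each) over all outcomes where the pooled chi-square test is significant.

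| Control v Gadoterate | Two-sided 5% | One-sided 5% |
|---|---|---|
| 2.5% v 5% | 18% | 31% |
| 5% v 10% | 35% | 49% |
| 10% v 20% | 64% | 76% |
| 15% v 30% | 85% | 91% |

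For 90% power (two-sided), the Gadoterate rate must reach 12.2% against 2.5%, 16.8% against 5%, or 24.5% against 10%. With a 5% control rate it would have to exceed the roughly 15% quoted for other agents.

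**3. What a favourable result leaves open.** The Newcombe interval combines the Wilson limits (l, u) of each rate. Its upper limit is d + √[(u_G − p_G)² + (p_C − l_C)²], where d = p_G − p_C.

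- *7 v 3 events:* p_G = 0.0515 (Wilson 0.0252 to 0.1024) and p_C = 0.0221 (0.0075 to 0.0629). The upper limit is 0.0294 + √(0.0510² + 0.0145²) = 0.082, and the lower is -0.019. Historical p = 0.0003; chi-square p = 0.20.
- *12 v 5 events:* interval -0.8 to 11.5 points; historical p = 0.023, chi-square p = 0.080, Fisher p = 0.13. This is the largest upper limit among outcomes that pass the historical test at 2.5% with a non-significant chi-square.

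**4. How often both readings are favourable** (12 or fewer Gadoterate events and a non-significant chi-square):

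| True rates, Gadoterate v control | Both favourable |
|---|---|
| 5% v 2.5% | 82% |
| 7.5% v 3.75% | 65% |
| 10% v 5% | 35% |
| 12.5% v 5% | 10% |
| 15% v 5% | 2% |

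At 5% v 2.5%, both are favourable with an upper limit above 7.5 points in 36% of trials, above 8 points in 27%, and above 10 points in 5%.

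**5. Precision available.** The Wald half-width with equal rates p is 1.96 × √[2p(1 − p)/136]: 5.2 points at 5% and 7.1 at 10%. By Newcombe it is 5.7 points with 7 v 7 events and 7.4 with 14 v 14.

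**The case against.** The strongest reply is that Statistics does contain a proper Aim 1 test. Safety would then rest on rejecting 15%, not on failing to reject something, and no sentence says that a non-significant cohort difference means safe. That stands as far as it goes: the historical test is sound and should be kept. It does not answer whether there is an excess over no contrast, which is the comparison that the note on pre-existing conditions invokes.

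Other points have some force:

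- *That note can be read as a remark about confounding, not about power to detect a doubling.* On that reading it is still wrong, because power does not correct confounding.
- *A comparison of mean GFR change would be more sensitive.* With 136 per cohort, a two-sided t-test has 90% power for about 0.39 standard deviations. Specific Aim 1 mentions analytic models, so such an analysis is possible. But Hypothesis 1 and the sample size are framed as event rates.
- *The examples depend on assumed rates and tests.* True. The 8.2-point limit for 7 v 3 is above the median for favourable results at 5% v 2.5%. If both true rates are 5%, both readings are favourable with an upper limit above 8 points in 16% of trials; if both are 2.5%, in 3.5%. The 11.5-point maximum depends on the test: with Fisher's test, 12 v 4 is also non-significant and its upper limit is 12.1.
- *The GFR fall that counts as an event is not defined.* Correct. That has to be settled for any Aim 1 analysis, including the historical one.
- *This is a pilot.* Also correct. It is why estimation, not a formal margin, is the right request.

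**Conclusion.** The concern holds and should be fixed. Hypothesis 1 is worded so that non-significance reads as safety. The only Aim 1 calculation is against an external rate, and the power relied on for the cohort comparison is neither calculated nor, for moderate excesses, present: 18% to 35% for a doubling from an assumed control rate of 2.5% to 5%. A true 10% v 5% would still give two favourable readings about one time in three. Large excesses are usually caught (2% missed at 15% v 5%), so the gap concerns moderate harm. The figures rest on assumed control rates, a yes/no event and an unadjusted comparison. The faults in wording and logic do not depend on them.

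**What to change.** 1. Restate Hypothesis 1 so that safety is not inferred from non-significance. Under Aim 1 or in Analysis, state that the Gadoterate-minus-non-contrast difference in renal event rate will be reported with its two-sided 95% confidence interval (for example Newcombe), whatever the p-value. The event definition must be fixed beforehand.
2. In the note after the exclusion criteria, replace the power claim with the expected precision: about ±5 to 6 points if both rates are 5%, and ±7 if both are 10%. Remove the suggestion that power deals with differences between self-selected cohorts.
3. Keep the comparison with the historical 15% as a separate, labelled test.

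Optional: a baseline-adjusted difference as a sensitivity analysis, with very few covariates, since only 2 × 136 × 0.05 = 13.6 events are expected at 5%. A margin for the upper limit is needed only if the sponsor wants a formal safety conclusion from the pilot, and it must be justified in advance. With both rates 5% and 136 per cohort, the chance that the Newcombe upper limit falls below the margin is 94% for 10 points, 74% for 7.5 and 41% for 5. A 5-point margin would need about 320 per cohort for 80% power or 430 for 90%, which belongs in the later trial.

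The cost is wording in three places, with no extra patients or data. The safety claim becomes harder to make.
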